#### 7.2.5 Visit 5 (Post-operative, Day 1)

##### Control group

The following will be performed as **routine (standard care)**:

- Neurological examination.

The following will be performed for the **research only**:

- Dialysate collection and blood sample collection.
- Collection of adverse events.

#### **Study drug group**

The following will be performed as **routine (standard care)**:

- Neurological examination.

The following will be performed for the **research only**:

- Patient will take study medication at 8am +/- 4 hours and then study medication will be discontinued.
- Comprehensive Metabolic Panel (which includes electrolytes, renal function and liver function) (approximately 1 teaspoon of blood). Lab values within 1.5x institutional upper limit of normal are acceptable and not considered adverse events.
- Dialysate and blood sample collection.
- Collection of adverse events.

#### **Microdialysis collection/monitoring**

After the imaging confirms proper placement of the MDC tip, the inlet tubing will be connected to a portable syringe pump to perfuse artificial CSF (Perfusion Fluid CNS, ref. no. P000151, CMA, Solna, Sweden) at a rate of 1.0  $\mu$ l/min. The inlet tubing of the catheter will be connected to a CMA 107 Microdialysis Pump (ref. no. P000127, CMA, Solna Sweden). A microvial will be connected at the end of the outlet tubing to collect perfusate.

Concurrently, a plastic microvial (Ref. No. P000001, CMA, Solna, Sweden) will be placed in the vial holder at the end of the outlet tubing to collect dialysate. This microvial can hold up to 200 $\mu$ L of fluid. It will need to be replaced with a new one every 3 hours. During daytime work week hours, trained research coordinators, in coordination with nursing team will collect dialysate and replace the microvials. At all other times, these tasks will be performed by the study PI, [name].

Dialysate sample collection will begin in the morning of postoperative day 1. If the participant was able to tolerate the AM dose of study drug (study drug group only), sample collection will begin immediately after drug administration. Otherwise, sample collection will begin within the same allotted time period (i.e. 8AM +/- 4 hours). For the control group, sample collection will be at 8 AM +/- 4 hours. The initial sample will be labeled as the 'Time 0' sample. Additional samples will be collected at 15 and 30 minutes, along with 1, 2, 4, 6, 8, and 24 hours after 'Time 0'.

Microvials containing the dialysate should be stored in an ultralow temperature freezer ( $\leq 70^{\circ}\text{C}$ ) until they can be batch analyzed by LC/MS/MS.

#### **Plasma collection**

As part of the standard of care, patients will have an arterial line placed at the time of biopsy or surgery, which is usually discontinued 24-48 hours postoperatively, upon evidence of hemodynamic stability.

Blood samples will be collected from the arterial line at the following times: At time of biopsy or tumor resection (day of surgery), 'Time 0' (aligned with dialysate sample collection time above), then 15 and 30 minutes, along with 1, 2, 4, 6, 8, and 24 hours after 'Time 0'.

Blood (3 mL) will be collected in green top tubes containing sodium heparin anticoagulant. The plasma collection tube will be promptly mixed by gently inverting 6-times, then placing it on wet ice, until centrifuged at 1,300 x g for 10 min at 4°C. Samples will be centrifuged for harvesting plasma as soon as possible after collection (within 1 hour). Upon centrifugation, the plasma will be separated from the blood cells using a pipette and transferred into an appropriately labeled polypropylene freezer vial. The samples should be processed to plasma within 30 minutes from centrifugation and the pH adjusted to <4 with the use of 8.5% phosphoric acid (15µL of 8.5% phosphoric acid per 0.5mL of plasma). Plasma will then be stored frozen at -70°C until subsequent batch analysis.

#### 7.2.6 Visit 6 (Post-operative, Day 2)

##### Control group

The following will be performed for the **research only**:

- Dialysate and blood collection will end at 8 am +/- 4 hours on post-op Day 2.
- Removal of microcatheters.
- Collection of adverse events.

Following completion of dialysate collection, the infusion pump use will cease and the MDC will be removed percutaneously at the bedside by a study team physician. The entry site of the catheter will be closed with a suture or steri-strip as necessary and a clean dressing applied. The patient will be kept in the hospital for observation until discharged by the primary neurosurgical team.

##### Study drug group

The following will be performed for the **research only**:

- Dialysate and blood sample collection will end at 8 am +/- 4 hours on post-op Day 2.
- Removal of microcatheters.
- Collection of adverse events.

Following completion of dialysate collection, the infusion pump use will cease and the MDC will be removed percutaneously at the bedside by a study team physician. The entry site of the catheter will be closed with a suture or steri-strip as necessary and a clean dressing applied. The patient will be kept in the hospital for observation until discharged by the primary neurosurgical team.

#### 7.2.7 Visit 7 (Post-operative follow-up 14+/-7 days)

##### Control group

The following will be performed as **routine (standard care)**:

- Neurological exam

The following will be performed for the **research only**:

- Collection of adverse events.

##### Study drug group

The following will be performed as **routine (standard care)**:

- Neurological exam

The following will be performed for the **research only**:

- Collection of adverse events.

Samples collected during the study for research-only purposes will be sent for analysis as shown below:

Sample	Analysis location
Comprehensive Metabolic Panel (which includes electrolytes, renal function and liver function) at Visits 1, 2, and 5	Clinical laboratory
Tissue from biopsy or surgery	[name] laboratory (pharmacodynamics)
	Mass Spectrometry core at Penn State Hershey Cancer Institute (PSHCl) (metabolites and drug concentration)
Plasma at Visits 5 and 6	Mass Spectrometry core at PSHCl (drug concentration)
Dialysate at Visits 5 and 6	Mass Spectrometry core at Penn State Hershey Cancer Institute (PSHCl) (metabolites and drug concentration)

**Schedule of events**

	Visit 1 (Screening and baseline)	Visit 2 (Day 3 +/- 2 days of azole)***^	Visit 3 (morning of and during biopsy or surgery)	Visit 4 (post-op Day 0)	Visit 5 (post-op Day 1)	Visit 6 (post-op Day 2)	Visit 7 (14 days +/- 7 days post-op)
Informed consent process	X						
Demographics +	X						
Medical history +	X						
Neurological Exam +	X			X	X		X
Concomitant medication review +	X		X ^				
Women only: Pregnancy test +, **	X						
12-lead ECG +	X						
MRI Brain +	X*						
Comprehensive Metabolic Panel (which includes electrolytes, renal function and liver function) ^	X	X			X		
CBC ^	X						
Study drug (posaconazole) dispensed ^	X		X#	X#			
Adverse Events (if any)		X	X	X	X		X
Microdialysis catheter placement			X				
Intraoperative blood and tissue collection			X				
CT scan of head +				X			
Dialysate collection					X	X	
Blood sample collection					X	X	
Microdialysis catheter removal						X	

+Performed as routine, standard care (see note about Visit 2) and used for research as well. Any investigations or clinical documentation within 31 days prior to screening are acceptable

\* Previously performed MRI Brain +/- Gadolinium contrast scan within 45 days prior visit 1 will be reviewed as baseline MRI

\*\* Only required for women who, in the investigator's opinion, are of childbearing potential

\*\*\* Only performed for study drug group participants who do not have biopsy or surgery within 3 days. This is a research-only visit and all activities at this visit are for research only.

^Only applicable to those participants in the study drug group.

#As inpatient. Study drug will be dispensed as inpatient on Visit 1 if patient already hospitalized; otherwise it will be outpatient

### 7.3 Duration of Participation

It will take participants a maximum of 31 days to complete this research study. They will be asked to attend the research site a maximum of 4 separate times.

### 7.4 Test Article(s) (Study Drug(s) and/or Study Device(s))

#### 7.4.1 Description

##### Classification:

Posaconazole is a second-generation triazole agent with a potent and broad antifungal activity. Posaconazole is available as concentrated solution to be diluted before intravenous administration, delayed-release tablet, or suspension for oral administration. Posaconazole is designated chemically as 4-[4-[4-[4-[(3R,5R)-5-(2,4-difluorophenyl)tetrahydro-5-(1H-1,2,4-triazol-1-ylmethyl)-3-furanyl]methoxy]phenyl]-1-piperazinyl]phenyl]-2-[(1S,2S)-1-ethyl-2-hydroxypropyl]-2,4-dihydro-3H-1,2,4-triazol-3-one with an empirical formula of C37H42F2N8O4 and a molecular weight of 700.8.

##### Pharmacokinetics of delayed-release Posaconazole tablets:

When given orally in healthy volunteers, posaconazole delayed-release tablets are absorbed with a median Tmax of 4 to 5 hours. The elimination half-life of posaconazole has been estimated to vary between 15-35 hours [56]. Steady-state plasma concentrations are attained by Day 6 at the 300 mg dose (QD after BID loading dose at Day 1).

The absolute bioavailability of the oral delayed-release tablet is approximately 54% under fasted conditions. The Cmax and AUC of posaconazole following administration of posaconazole delayed-release tablets is increased 16% and 51%, respectively, when given with a high fat meal compared to a fasted state. In order to enhance the oral absorption of posaconazole and optimize plasma concentrations, posaconazole delayed-release tablets should be administered with food.

#### 7.4.2 Treatment Regimen

The timing of study drug administration will be based on the scheduled date and time of biopsy or surgery, which will occur within 7-10 days of Visit 1. The latter parameter is based on the drug half-life, as follows:

- Participants will be taking posaconazole as 300mg PO BID in the first day, followed by 300mg PO once daily thereafter.
- The mean elimination half-life of posaconazole is 26-31 hours (product monograph). Therefore, posaconazole will reach steady state at approximately 130-155 hours following the first dose (5 half-lives). As such, we will work backwards from the scheduled date and time of biopsy or surgery such that participants in the posaconazole arm will receive drug for 168-240 hours. The upper range of the dosing (240 hours) is to minimize potentially unnecessary exposure to drug while accounting for variability in half-life measurements.

In order to maintain steady-state concentrations, study drug will be administered at the following times as well:

1. On the morning prior to planned surgical intervention
2. On the morning of postoperative day 1, at 8:00AM +/- 4 hours \*

\*Only if postoperative CT rules out complications and the MDC(s) are correctly positioned.

#### 7.4.3 Method for Assigning Subject to Treatment Groups

Not applicable, as this is an open label, non-randomized Phase 0 feasibility trial.

#### **7.4.4 Subject Compliance Monitoring**

Nursing staff will chart administration of study drug into the patient's EMR and study personnel will monitor and document the completion of all study procedures. In the outpatient setting, participants will be provided with a medication diary.

#### **7.4.5 Blinding of the Test Article**

Not applicable, as this is an open label, non-randomized Phase 0 feasibility trial.

#### **7.4.6 Receiving, Storage, Dispensing and Return**

##### **7.4.6.1 Receipt of Test Article**

A study specific supply of FDA-approved posaconazole 100mg tablets will be purchased from a pharmacy wholesaler for use in this study. The manufacturer, lot number, and expiration date of the purchased posaconazole tablets will be maintained in the drug accountability records kept by the IDS pharmacy.

##### **7.4.6.2 Storage**

IDS pharmacy will store the posaconazole tablets at controlled room temperature as per the USP guidelines for controlled room temperature.

##### **7.4.6.3 Preparation and Dispensing**

Once an enrolled subject's biopsy or surgery date is scheduled, subjects will receive an outpatient supply of the posaconazole tablets to take beginning ~130-155 hours prior to biopsy or surgery. Subjects will take six posaconazole 100mg tablets by mouth, once in the morning and once in the evening, on the first day followed by three 100mg tablets by mouth daily. The last dose from the outpatient supply will be taken on the morning of the biopsy or surgery. Subjects should return any study medication remaining when they arrive the day of biopsy or surgery. Post-biopsy or surgery subjects will receive one additional dose of posaconazole 300mg (three 100mg tablets) from the study supply, in the morning after biopsy or surgery. These doses will also be dispensed from a study specific supply. The medication vial should be return to IDS for accountability.

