### **Study drug group**

Participants will be given 12 days' worth of the study drug (pills) and verbally instructed how and when to take them. The prescription bottle will have a label with this information on it as well.

The timing of study drug administration will be based on the scheduled date and time of biopsy or surgery, which will occur within 7-10 days of Visit 1. The latter parameter is based on the drug half-life, as follows:

- Participants will be taking posaconazole as 300mg PO BID in the first day, followed by 300mg PO once daily thereafter.
- The mean elimination half-life of posaconazole is 26-31 hours (product monograph). Therefore, posaconazole will reach steady state at approximately 130-155 hours following the first dose (5 half-lives). As such, we will work backwards from the scheduled date and time of biopsy or surgery such that participants in the posaconazole arm will receive drug for 168-240 hours. The upper range of the dosing (240 hours) is to minimize potentially unnecessary exposure to drug while accounting for variability in half-life measurements.

In order to maintain steady-state concentrations, study drug will be administered at the following times as well:

1. Pre-operatively on the morning of the planned surgical intervention
2. On the morning of postoperative day 1, at 8:00AM +/- 4 hours \*

\*Only if postoperative CT rules out complications and the MDC(s) are correctly positioned.

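### Section 7.4.6.3 starts posaconazole about 130-155 h before surgery where the regimen requires 168-240 h, and its day-1 sentence can be read as 1,200 mg instead of 600 mg

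*Combined protocol and SAP*

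**What the plan says.** Sections 7.2.1 (Study drug group) and 7.4.2 give the same regimen:

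- Dose: "Participants will be taking posaconazole as 300mg PO BID in the first day, followed by 300mg PO once daily thereafter".
- Time to steady state: "posaconazole will reach steady state at approximately 130-155 hours following the first dose (5 half-lives"), from a mean half-life of 26-31 h.
- Duration, counted back from surgery: "participants in the posaconazole arm will receive drug for 168-240 hours". The upper limit is meant to restrict exposure while allowing for variation in half-life.
- Scheduling: "biopsy or surgery, which will occur within 7-10 days of Visit 1".
- Supply (7.2.1 only): "Participants will be given 12 days" of tablets.

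Section 7.4.6.3 (Preparation and Dispensing) differs:

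- Start: subjects get an outpatient supply to "take beginning ~130-155 hours prior to biopsy or surgery".
- Day 1: "Subjects will take six posaconazole 100mg tablets by mouth, once in the morning and once in the evening, on the first day", then three tablets daily.

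Section 7.4.1 gives a wider half-life range: "The elimination half-life of posaconazole has been estimated to vary between 15-35 hours".

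**The concern.** **Start time.** The regimen uses 130-155 h as an intermediate result and then requires a longer course. Section 7.4.6.3 uses the intermediate result as the start of dosing. No start time satisfies both, so every treated patient departs from one section or the other.

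**Day-1 dose.** Taken literally, six tablets on each of two occasions is 12 tablets, twice the intended load. This is the only place where the protocol states day 1 as a number of tablets, and it stands in the section that governs dispensing. Dosing is mostly outpatient and self-administered. Visit 2 falls 1-5 days after the start (7.2.2), and the medication diary is first checked on the day of surgery (7.2.3). Both come after the day-1 doses.

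**Evaluability.** Section 8.2 (Study Population) makes dosing to protocol specifications a condition for inclusion in the analysis, and the protocol holds two specifications. This is secondary: section 8.3 (Off Study Criteria) removes patients only after more than 3 missed doses.

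**Working it through.** **1. The plan's own figure.** 5 × 26 h = 130 h and 5 × 31 h = 155 h, so the stated time to steady state is reproduced. The error lies in how 7.4.6.3 uses it.

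**2. The two windows.** 7 × 24 = 168 h and 10 × 24 = 240 h, so the required duration matches surgery 7-10 days after Visit 1. Shortfall of 7.4.6.3 against the minimum: 168 − 155 = 13 h to 168 − 130 = 38 h.

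Administrations at 0 and 12 h, then every 24 h through the morning of surgery:

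| Start before surgery | Administrations | Dosing days |
|---|---|---|
| 130 h | 7 | 6 |
| 155 h | 8 | 7 |
| 168 h | 9 | 8 |
| 240 h | 12 | 11 |

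Section 7.4.6.3 is therefore 1-2 administrations below the minimum of 9. The 12-day supply fits 8-11 dosing days better than 6-7.

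**3. Day-1 dose.** Regimen: 2 × 300 mg = 600 mg (6 tablets). Section 7.4.6.3 read per occasion: 2 × 6 × 100 mg = 1,200 mg (12 tablets). Read as a day total: 600 mg.

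**4. Effect on concentration.** Assumption: one-compartment bolus model with linear superposition. With k = ln 2 / half-life, the amount at time t is the sum over doses D given at times s of D × exp(−k(t − s)). The steady-state peak is 300 / (1 − exp(−24k)). Half-lives are 15 and 35 h (7.4.1) and 26 and 31 h (7.4.2).

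| Half-life | 15 h | 26 h | 31 h | 35 h |
|---|---|---|---|---|
| After second day-1 dose ÷ steady-state peak, 600 mg | 1.06 | 0.82 | 0.73 | 0.68 |
| Same, 1,200 mg | 2.11 | 1.63 | 1.47 | 1.35 |
| Course maximum ÷ steady-state peak, 600 mg | 1.28 | 1.07 | 1.00 | 1.00 |
| Same, 1,200 mg | 2.11 | 1.66 | 1.54 | 1.45 |
| Pre-operative AUC, 1,200 vs 600 mg, 130 h start | 1.329 | 1.359 | 1.369 | 1.376 |
| Concentration at surgery, 1,200 vs 600 mg, 130 h start | 1.007 | 1.046 | 1.066 | 1.081 |
| Postoperative day-1 AUC, 1,200 vs 600 mg, 130 h start | 1.002 | 1.024 | 1.038 | 1.050 |
| Level at surgery ÷ steady state, 600 mg, 130 h start | 1.003 | 1.005 | 0.997 | 0.987 |

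The course maximum rises by about 45% (35 h) to 65% (15 h). If the literal load were combined with the regimen's 168 h start, pre-operative AUC would rise by 27-30%, concentration at surgery by at most 3% and the postoperative day-1 AUC by at most 2%.

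**5. Would the supply run out?** The documents give no tablet count. If 12 days is counted on the 600 mg load, it is 6 + 11 × 3 = 39 tablets. Literal use through the morning of surgery is 12 + 5 × 3 = 27 (130 h start) or 12 + 6 × 3 = 30 (155 h). With the regimen's longer starts it is 33 (168 h), 39 (216 h) or 42 (240 h). A patient following 7.4.6.3 literally would not run short, so the supply gives no warning.

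**The case against.** The strongest reply is that the certain error is almost harmless and the harmful one is only an ambiguity.

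- *The late start barely matters.* This stands. The level at surgery is about 99-100% of steady state with the loading dose, and 7.4.1 itself puts steady state at Day 6.
- *The intent is plainly 600 mg.* This also stands. Sections 7.2.1 and 7.4.2 say 300 mg twice on day 1. Section 7.4.6.3 itself equates 300 mg with three tablets for the postoperative dose. The dose-modification table in 18.2 has no 600 mg unit dose. These cues show what was meant, but they do not correct the sentence.
- *Patients do not dose from the protocol.* They receive verbal instruction, a labelled bottle and a diary, and inpatients have doses charted by nursing staff. This lowers the risk. It is no evidence of a label error, but the wording of those materials is not in the documents, so it cannot be relied on to remove the ambiguity either.
- *Harm is not shown.* Agreed. No toxicity threshold for 1,200 mg is given.
- *The figures for starts of 168 h or more mix two sections.* Fair. The 1,200 mg reading arises only in 7.4.6.3, so the 130-155 h figures are the ones that follow from that section as written.

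**Conclusion.** The concern holds on both counts and should be corrected. The start windows in 7.4.6.3 and 7.4.2 cannot both be met: the gap is 13-38 h, or 1-2 administrations. The day-1 sentence permits a reading at twice the intended dose, 1,200 mg against 600 mg.

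The importance rests on an ambiguous dosing order, not on bias in the primary endpoint. Under the one-compartment assumption, a literal double load with the 130 h start adds at most 8% to concentration at surgery and 5% to the postoperative day-1 AUC. Its effect is early: a course maximum about 45-65% higher and a pre-operative AUC 33-38% higher. Clinical harm at 1,200 mg is not quantified. Routine exclusion of patients is not shown either, since 1-2 doses is below the limit of more than 3.

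**What to change.** Replace the dosing instruction in 7.4.6.3 with: *three 100 mg tablets in the morning and three in the evening on day 1 (600 mg in total), then three tablets once daily, beginning 168-240 h before surgery.* Check the bottle label and the medication diary against that sentence.

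Two optional additions: check the dispensed tablet count (39 for 12 days on the 600 mg load), and state in 8.2 that the dosing specification is the one in 7.4.2 and how it relates to the missed-dose limit in 8.3.

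The cost is a one-sentence amendment and a check of the label and diary, plus one clause in 8.2 if that addition is made. No design change, extra patients or extra visits are needed.

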##### **7.4.6.4 Return or Destruction of the Test Article**

Any dispensed but not administered tablets will be noted in the accountability records and subsequently destroyed.

##### **7.4.6.5 Prior and Concomitant Therapy**

A concomitant therapy is any medication which is administered between study enrollment and the end of the study drug treatment phase that could achieve a synergistic/antagonistic effect or increase the risk of adverse drug interactions. Situational medications or dose required during the surgical procedures will not be logged. All other therapies will be monitored daily and recorded by study team members during the duration of the treatment phase with the study drug.

The following is a list of contra-indications to the use of posaconazole, as obtained from the product monograph (this list is not all-inclusive):

- Patients who are hypersensitive to this drug or to any ingredient in the formulation or component of the container. For a complete listing, see the Dosage Forms, Composition and Packaging section

of the product monograph. There is no information regarding cross-sensitivity between NOXAFIL® and other azole antifungal agents. Caution should be used when prescribing NOXAFIL® to patients with hypersensitivity to other azoles.

- Co-administration of NOXAFIL® and ergot alkaloids. NOXAFIL® may increase the plasma concentrations of ergot alkaloids, which may lead to ergotism.
- Co-administration of NOXAFIL® and certain medicinal products metabolized through the CYP3A4 system: terfenadine, astemizole, cisapride, pimozide, and quinidine. Although not studied *in vitro* or *in vivo*, co-administration of these CYP3A4 substrates may result in increased plasma concentrations of those medicinal products, leading to potentially serious and/or life-threatening adverse events, such as QT prolongation and rare occurrences of torsade de pointes.
- Co-administration of NOXAFIL® and HMG-CoA reductase inhibitors (statins) that are primarily metabolized through CYP3A4, since increased plasma concentration of these drugs can lead to rhabdomyolysis.
- Co-administration of NOXAFIL® and sirolimus. Concomitant administration of NOXAFIL® with sirolimus increases the sirolimus blood concentrations by approximately 9-fold and can result in sirolimus toxicity.

The following is a full list of drugs that alter the plasma concentration of posaconazole obtained from the product monograph:

- Rifabutin
- Phenytoin
- Efavirenz
- Fosamprenavir
- Glipizide
- Loperamide
- Antacids/H2 receptor antagonists
- Cimetidine
- Esomeprazole
- Metoclopramide

